possible seizures), or death. In 1 out of 40 rats treated with very high doses of POMA for 6 months, areas of brain injury were observed. Mice treated with POMA also showed uncontrollable and rapid shaking (convulsions or possible seizures). Vomiting, soft or watery stools, and/or a severe rash were seen in monkeys given high doses of POMA for up to 1 year. A single monkey was euthanized due to severe skin rash on Day 235 of the 1-year study. No convulsions have been observed in monkeys. In a study of the effects of POMA on pregnant rats and their offspring, some baby rats had significant decreases in their body weight, and some baby rats died up to 14 days after birth. The levels of drug in subject's blood will be lower than the levels of drug in monkeys at which the above bad effects were noted. Effects of convulsion observed in rats and mice were observed at blood drug levels that are similar to or lower than the levels expected in this study.

Summary

Doses of POMA as high or higher than the highest dose in this study (160 mg twice a day) have been taken by 24 healthy people without psychiatric illness for 10 days in a previous study without significant side effects. 44 patients with schizophrenia completed a multiple dose escalation study over a dose range of 160 to 480 mg BID for 7 days. Therefore, this dose and higher has been given before, but not for this length of time (14 days, though 7 and 10 days have been given).

2) Interviews and ratings (general): Study participants may feel anxious during medical history interviews or during administration of specific rating scales.

3) Brain imaging scans (general): It may be uncomfortable to lie motionless in the MRI scanner and it may cause some subjects to feel anxious.

4) Intravenous catheter: Intra-venous lines can cause pain, bleeding, or occlusion/clotting.

5) MRI Imaging: The Magnetic Resonance (MR) scanner uses strong magnetic fields and radio waves to take measurements in the brain. MRI involves lying on a table that slides into a large magnet shaped like a cylinder. Before beginning the procedure, we will determine that patients do not have a pacemaker or any unsafe metallic implants such as an aneurysm clip or heart valve and certain tattoos, and they will be asked to remove any metal or magnetized objects (such as keys, chains, jewelry, retainers, medication patches, hairpins or credit cards). In addition, they will complete a brief interview at the time of study inclusion to determine if they have Asthma or a history of renal failure that may exclude their ability to receive an injection of Gadolinium (see below section). These questions will be repeated on the day of the scan.

For the scanning procedure, they will be asked to lie flat on the back in the MRI scanner for approximately 60 minutes and to remain as still as possible. Some people have reported sensations during MRI scans, such as "tingling" or "twitching" (or, very rarely, a painful sensation), which are caused by changes in the magnetic field that can stimulate nerves in the body. With any MRI scan, on occasion, some people experience nervousness or discomfort due to the scanner's small space and the need to lie still. Except for

pacemakers, some types of metallic implants, and medication patches, we are not aware of any other potentially dangerous interactions or hazards associated with the MRI scan. The MRI scanner also produces a loud noise.

6) Gadolinium compounds do have side effects, we use Dotarem. One side effect of gadolinium is nausea and vomiting, observed in less than 2 people out of every 100 injected. (1.8% estimate). Dry mouth (less than 2%), dizziness (0.7% up to 3.6%), and headache (2.2% up to 5.8%) are infrequent, yet possible side-effects. An additional side effect is hives, observed in less than 1 person out of every 100 injected with gadolinium. All of these side effects resolve within 20 minutes to several hours. People with asthma or known sensitivities to contrast agents are at increased risk for more serious side rare side effects (less than 1/10,000 injections estimate), such as severe allergic reaction that may result in sudden difficulty breathing, and therefore will not be injected with Gadolinium. Some patients with acute renal failure or end-stage renal disease have developed a serious medical condition known as nephrogenic systemic fibrosis (NSF) after the use of gadolinium for MRI. The primary concern regarding risks to renal function from gadolinium-based contrast agents (GBCAs) is specific to this population of patients who have end-stage renal disease (ESRD) on hemodialysis, or acute, florid, clinical renal failure, and then are exposed to gadolinium. This population of patients is by definition excluded from this study by virtue of medical history and general review of systems. Renal dysfunction as a result of gadolinium in a population without history of end-stage renal disease or acute renal failure has not been described in the medical literature. In a retrospective study conducted at two large medical centers, 74,124 patients were injected with a standard dose of gadolinium (0.1mmol/kg, the same dose used in our research studies) who had no screening for renal function, with a rate of zero/74,124 cases of renal complications (e.g., nephrogenic systemic fibrosis (NSF) or other renal dysfunction) post injection (Prince, Zhang et al. 2008). All 15 cases of NSF that were found in this retrospective study all had severe, clinical renal failure at the time of gadolinium injection. No cases of NSF have been identified in persons with normal renal function or with moderate renal dysfunction.

Regarding this specific risk, the FDA recommends:

1. Become familiar with the patient populations at risk for NSF.
2. Avoid using gadolinium in patients with known risks for developing NSF.
3. Prior to administering gadolinium, evaluate patients for renal dysfunction by assessing their renal function, either by obtaining a medical history or conducting laboratory tests that measure renal function.
4. When administering gadolinium, do not exceed the recommended dose in product labeling and allow a sufficient period of time for elimination of the agent from the body prior to any further gadolinium administration. The American College of Radiology recommends, as of July 2007, pre-screening patients prior to the administration of Gadolinium-Based MR Contrast Agents (GBMCA) their glomerular filtration rate (GFR) for the following patient groups:

1. Renal disease (including solitary kidney, renal transplant, renal tumor)
2. Age >60
3. History of Hypertension
4. History of Diabetes
5. History of severe hepatic disease/liver transplant/pending liver transplant. For patients in this category only, it is recommended that the patient's GFR assessment be nearly contemporaneous with the MR examination for which the GBMCA is to be administered. Concurrently, researchers investigating clinical

risk factors as well as the role of gadolinium formulation in development of NSF (Peak and Sheller 2007; Kanal, Broome et al. 2008) note that the Gadolinium-based contrast agents may possess differential risk of NSF depending upon their chemical structure. Gadolinium agents are classified on the basis of chelate biochemical structures (macrocyclic vs linear) and chelate charge (ionic vs nonionic) (Perazella 2007). Macrocyclic molecules bind gadolinium more tightly than do linear chelates, possess high thermodynamic conditional stability, and have lower dissociation rates. Ionic cyclic chelates are thought to be the least likely to release free gadolinium, whereas nonionic linear chelates are the most likely to release free gadolinium in the body. Risk of NSF is considered to be the highest with Omniscan and OptiMARK, which carry no molecular charge, are arranged in a linear structure with excess chelate, and seem more likely to release free gadolinium into the body. Since gadodiamide (Omniscan) has been most commonly associated with NSF (Thomsen 2006) and gadopentetate dimeglumine (magnevist) second-most associated; the Neurological Institute's imaging center has changed contrast agents from Omniscan to Dotarem, a macrocyclic ionic agent.

The dosing guidelines for the brand of gadolinium to be used in this study are as follows: CNS (Central Nervous System) Adults: The recommended dose of Dotarem 0.1mmol/kg (0.2 mL/kg) administered as a rapid bolus intravenous injection. According to the Multihance package insert and the recent literature, repeated dosing of mutihance up to a total dose of .3mmol/kg (in three doses of 0.1mmol/kg) can be immediate given within a short time-span with no adverse effects. The elimination half-life of the compound is 1-2 hours. Prior to readministration, the FDA recommends 'sufficient time for drug elimination'. Our study design of a single baseline dose at 0.1mmol/kg followed by repeated injection 2 weeks later is more than adequate time for elimination of contrast agent, which should be complete by two days, and is well below the maximal dosing guidelines that have been shown to be safe with repeated dosing in prior studies.

COVID Risks There is a risk of exposure to COVID when deciding to go out in public and travel for research.

Describe procedures for minimizing risks

- 1) POMA: In order to minimize risk, we will exclude any individual with any history of seizure disorder, or any severe medical condition. We will obtain frequent laboratory analyses, including liver tests, and cbc, adverse event queries, and EKGs and temperature during this study. Patients will be terminated from the study if they develop side effects that are, in the opinion of the PI, preclusive of continuing in this protocol or in particular if they meet worsening criteria based on the CGI or need for prn medications.
- 2) Interviews and ratings (general) Participants will be allowed to take breaks as necessary and are not required to answer any questions that may be uncomfortable.
- 3) Brain imaging scans (general): Our staff will be available to provide support, reduce anxiety, optimize the comfort of the subject and remove the subject from the MRI magnet bore if requested.
- 4) Intravenous catheter: Placement risks are minimized by using proper techniques.

5) MRI Imaging: Before beginning the procedure, we will determine that patients do not have a pacemaker or any unsafe metallic implants such as an aneurysm clip or heart valve and certain tattoos, and they will be asked to remove any metal or magnetized objects (such as keys, chains, jewelry, retainers, medication patches, hairpins or credit cards). In addition, they will complete a brief interview at the time of study inclusion to determine if they have Asthma or a history of renal failure that may exclude their ability to receive an injection of Gadolinium (see below section). These questions will be repeated on the day of the scan. The MRI scanner also produces a loud noise; earplugs will be provided to reduce this discomfort. If a patient experience any discomfort and wish to stop the scan, he/she can tell the MRI technologist who will stop the scan immediately. In our experience, no one has had sensations from the MRI that did not stop when the scanning stopped.

6) Gadolinium -A trained physician will inject the gadolinium and remain with the patient for the entire duration and for 15minutes after the scanning session is complete. Prior to scan, all participants being considered for participation in this study will continue to have a complete medical history prior to MRI to screen for renal failure/history of renal disease, diabetes, or hypertension, as well as screening labs. Patients with a diagnosis of acute renal failure are invariably severely medically ill and hospitalized, and are not eligible for study participation. In the current protocol, we administer Dotarem according to the patient's weight at a dose of 0.1mmol/kg. Based upon the amount administered, we do not exceed the recommended dosage. In addition, an Epi Pen will be available at all times during scanning with gadolinium.

COVID Risks: We will instruct subjects to wear a mask in public and while traveling, practice hand hygiene, and stay at least 6 feet away from others. We will tell subjects that if they do not feel comfortable traveling to the medical center for an appointment, for example if the subway or bus they would normally take is crowded, they can reschedule, or we may be able to arrange alternative transportation (if it is the case that alternative transportation, such as Uber or Lyft, can be offered). We have also minimized in-office visits to lessen this risk. We will keep our subjects informed about current public health recommendations, such as federal and local government guidelines and directives.

Methods to Protect Confidentiality

Describe methods to protect confidentiality

All records of the participating subjects will be kept in a locked room with access provided only to staff members. All data collected will be kept confidential and used for professional purposes only. Publications using these data will be done with only deidentified data. As this study is an intervention study utilizing an IND there is a possibility that the FDA will inspect our records.

When done remotely, we will use redcap to obtain consent on the cfs and hipaa forms. When sending electronic messages to subjects, we will only use encrypted email (NYSPI encrypted) and when

sending attachments with PHI only use the NYSPI secure file transfer website (<https://attach.nyspi.org/>) or encrypted nyspi email or redcap.

When COPE staff work from home, we all use the nyspi onedrive sharepoint system for storing documents or HIPAA compliant storage devices for paper documents. When conducting remote visits, we will use telephone or hipaa compliant video conferencing.

Will the study be conducted under a certificate of confidentiality?

Yes, we have already received a Certificate of Confidentiality

Direct Benefits to Subjects

Direct Benefits to Subjects

There are no direct benefits for participating patients.

Compensation and/or Reimbursement

Will compensation or reimbursement for expenses be offered to subjects?

Yes

Please describe and indicate total amount and schedule of payment(s).

Include justification for compensation amounts and indicate if there are bonus payments.

COVER PAGE

STATISTICAL ANALYSIS PLAN

OFFICIAL TITLE: Glutamate Reducing Interventions in Schizophrenia

NCT NUMBER: NCT03321617

DATE OF DOCUMENT: September 2, 2021

Statistical Analysis

Sample size and randomization: For the sample (n=3 subjects per 4 doses) the randomization sequences will be balanced in blocks of 4.

Primary outcome: Change (hypothesized decrease) in left CA1 CBV from baseline to 14 days.
Adherence, dropouts, and missing data: As this is a dose finding trial it is highly important that analyses be done on subjects who adhere closely to taking the study drug across the 14 days and who have complete data. We have set a threshold of adherence at >80% compliance. Subjects who are non-adherent, dropout, or who have unusable CA1 values at baseline or 14 days will be replaced.

Hypothesis testing (Go No-Go Criteria): The hypothesis to be tested is that at least one of the 4 doses shows a mean decrease in left CA1 CBV from baseline to 14 days of at least 0.33 standard deviations. Given that this is a dose finding study, to confirm the hypothesis we will not require a statistically significant test (e.g. $p < .05$), but instead will require the estimated mean decrease across the 3 patients in any one dose to be at least 0.33 standard deviations (standardized change will be used as the effect size measure). One-way ANOVA of the change scores on the 4 dose levels will be used to estimate the mean changes for each dose level standardized by the pooled standard deviation of change. Based on our prior data, the test-retest reliability of CA1 CBV (taken across 3 weeks in 4 patients on placebo) is very high (ICC = 0.85) providing confidence in the specificity of our measure of change and justification for including 3 patients at each level.

The target mean decrease of 0.33 standard deviations was chosen based on: 1) it represents half of the difference found between healthy controls and CHR patients in previous work and 2) we expect any decrease in CA1 CBV to be related to improvement in symptoms given our finding of a linear relationship between CA1 CBV and symptoms in CHR.

Similar analyses will be conducted for our secondary measures of hippocampal Glx (MRS). The clinical symptoms (SIPS) and cognitive measures (Matrics) are measured at 7 and 14 days and will be modeled with repeated measures ANOVA summarizing average change by dose over the study period. The safety measures (e.g. side effects) will be measured similarly throughout the study and will similarly be modeled with repeated measures ANOVA providing estimates at each time point and also aggregated across the study.

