To address these limitations of prior studies, we will administer several doses of POMA (low and high doses) over 14 days to individuals at clinical high risk for developing psychosis and use MRI brain imaging to determine whether these doses of POMA are affecting glutamate levels. In a second phase, we will use the dose of POMA that is found to decrease glutamate levels in a clinical trial in which we compare that dose of POMA with placebo in a standard clinical trial.

We will also perform a study to examine the stability of our MRI measures over up to 4 months in a healthy control population.

Background, Significance and Rationale

Background, Significance and Rationale

Studies suggest that abnormal elevations in extracellular glutamate can act as a pathogenic driver of schizophrenia, including in the hippocampus a brain region that neuroimaging studies suggest might be affected first and foremost. If this formulation is correct, then high glutamate should be considered a molecular target for drug discovery and agents that reduce extracellular glutamate should be an effective intervention. Pomaglmetad methionil (which we will call 'POMA') is one such agent, because as an agonist of presynaptic metabotropic glutamate 2/3 receptors this class of drug has been found to reduce glutamate release. Nevertheless, trials that have used POMA have to date shown little efficacy in patients with schizophrenia. Despite these failures, we believe that, based on the accumulative evidence, high glutamate is indeed a valid target and that two reasons might account for these initial failures. First, as these trials did not use a reliable brain biomarker of glutamate elevations there was no readout of 'target engagement', and thus it remains possible that these trials were false negatives. Second, and more importantly, schizophrenia is now thought to start in a prodromal phase before the onset of psychosis, and there is evidence to suggest that the prodromal stage might represent a unique time-window for therapeutic interventions, and so it possible that the drug was given at the wrong stage of the disease.

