Pathophysiological support for these conclusions comes from our studies (Schobel et al, Neuron, 2013) in which we applied fMRI indicators of metabolism and volumetric MRI to patients in prodromal stages of the disease who then progressed to the psychotic stage, and to a mouse model of the disease. Collectively, these studies suggested that glutamate is a driver of hippocampal dysfunction, that fMRI measures are sensitive to glutamate elevations, and that glutamate-reducing drugs can ameliorate hippocampal

dysfunction. We also have completed preliminary studies using magnetic resonance spectroscopy, in which we show that hippocampal glutamate is elevated in prodromal stages of the disease.

Based on the results of these and other studies, we have recently proposed a mechanistic model of disease progression (Small, Neuron, 2014), which predicts that because of its distinct pathophysiological features the prodromal stage of disease is a unique time-window that is most amenable to glutamate-reducing interventions. This mechanistic model motivates this protocol in which we hypothesize that: 1) MRI based measures of hippocampal metabolism and glutamate can be used as in vivo biomarkers of target engagement when using a glutamate-reducing intervention. 2) Glutamate-reducing interventions will be most effective when administered to prodromal patients, and only when they are shown to engage their target. The R61 phase of this proposal is designed to test the first hypothesis, and the R33 phase is designed to the second. The current IRB describes the R61 phase.

We will also perform a study to examine the stability of our MRI measures over up to 4 months in a healthy control population.

Specific Aims and Hypotheses

Specific Aims and Hypotheses

To perform a double-blind, randomized, phase Ib, multiple dose trial of 14 days of treatment with POMA (40mg bid, 80mg bid, 120mg bid, 160mg bid) in clinical high risk patients to determine which dose, if any, reduces hippocampal glutamate and metabolism using MRI techniques. The GO NO-GO decision will be whether or not any dose tested in the R61 phase of the trial decreases left CA1 CBV.

To examine the stability of our MRI measures over up to 4 months in a healthy control population.

Description of Subject Population

Sample #1

Specify subject population

Clinical High Risk

Number of completers required to accomplish study aims

12

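### The Go/No-Go rule gives a Go about 74% of the time for an inert drug (about 50% if 0.33 is a cross-sectional SD); the ICC does not justify three patients per dose, and a Go is not confirmation

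*SAP*

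**What the plan says.** The SAP's paragraph on hypothesis testing (Go No-Go Criteria) sets the decision rule for left CA1 CBV, baseline to day 14, with three patients on each of four active doses. It says that "to confirm the hypothesis we will not require a statistically significant test" and that it "instead will require the estimated mean decrease across the 3 patients in any one dose to be at least 0.33 standard deviations". The one-way ANOVA is to "estimate the mean changes for each dose level standardized by the pooled standard deviation of change".

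The number per dose rests on a test-retest ICC of 0.85 from four placebo patients over three weeks, described as "providing confidence in the specificity of our measure of change and justification for including 3 patients at each level". The 0.33 target is explained partly on the ground that "it represents half of the difference found between healthy controls and CHR patients in previous work". The SAP states no false-Go rate, no probability of a Go under a real effect, and no interval.

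The Protocol's Specific Aims give the decision without the threshold: "The GO NO-GO decision will be whether or not any dose tested in the R61 phase of the trial decreases left CA1 CBV". Its Lay Summary says what follows: "we will use the dose of POMA that is found to decrease glutamate levels in a clinical trial", comparing that dose with placebo.

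**The concern.** The rule takes the best of four very small groups and compares its point estimate with a cut-off that is small relative to the noise. Such a rule can pass often by chance, and the SAP does not say how often.

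Three things follow:

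- If a Go is likely whether or not the drug does anything, it cannot confirm that any dose engages the target, yet the SAP uses the word confirm.
- The ICC is the only support offered for three patients per dose, and it is not clear that reliability has any bearing on the error rate of a rule that divides by the SD of change.
- The unit of 0.33 is uncertain. The rule uses the SD of change, while half of a difference between controls and patients suggests a cross-sectional SD.

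This is the decision on which the R61 phase ends, and it opens the way to the placebo-controlled trial.

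**Working it through.** **Inputs (SAP, Statistical Analysis).** Four doses; three evaluable patients each, since dropouts, non-adherent patients and unusable scans are replaced; cut-off 0.33; divisor the pooled SD of change, with 4 × (3 − 1) = 8 df; ICC 0.85. The plan gives no error rate or power to reproduce. The only check available is 4 × 3 = 12, which matches the Protocol's 12 completers.

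**Assumptions.** Change scores are normal and independent with a common SD, and there is no drift over time.

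**Rule as written, inert drug, SD treated as known.**
- Standard error of a three-patient mean, in SD-of-change units: 1/√3 = 0.577.
- Cut-off in standard errors: 0.33 × √3 = 0.572.
- One dose passes: 1 − Φ(0.572) = 0.284.
- At least one of four passes: 1 − 0.716⁴ = 0.737.

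**Rule as written, SD estimated.** The four standardized means share one estimated SD, so the calculation integrates over a chi-square with 8 df. One million simulated trials agree.

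| Truth | P(Go) | Ratio to inert drug |
|---|---|---|
| No effect | 0.741 | – |
| One dose at 0.33 SD of change | 0.818 | 0.818/0.741 = 1.10 |
| All four at 0.33 SD of change | 0.936 | 0.936/0.741 = 1.26 |
| Any effect, however large | at most 1 | 1/0.741 = 1.35 |

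The ratio is the factor by which a Go multiplies the odds of that effect. With one active dose at 0.33, that dose itself passes 51% of the time. It shows the largest decrease in 43% of Gos; guessing would give 25%.

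**Role of the ICC.** With equal variances on both occasions, SD of change = cross-sectional SD × √(2(1 − ICC)). Better reliability shrinks the change scores and the divisor together, so under no effect the standardized mean has the same distribution at any ICC. Simulating paired scans at ICC 0.85 again gives 74%. A higher ICC does raise P(Go) for a fixed raw effect, but it does not lower the false-Go rate.

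**Cross-sectional reading.** √(2 × 0.15) = 0.548, so the cut-off becomes 0.33/0.548 = 0.602 SD of change.
- Inert drug, SD known: 1 − Φ(0.602 × √3)⁴ = 0.474.
- Inert drug, SD estimated from the 12 baseline values: 0.49 to 0.50.
- One dose at target: 0.70. All four at target: 0.93.
- Here the ICC matters. With the SD known, the false-Go rate is 0.61, 0.47 and 0.13 at assumed ICCs of 0.75, 0.85 and 0.95.

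**Drift.** There is no placebo arm. A common drift of 0.1 SD of change moves the 74% to 65% (upward) or 82% (downward).

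**Precision.** The 95% CI half-width for each dose mean is t(0.975, 8 df) × 0.577 = 2.306 × 0.577 = 1.33 SD of change, about four times the cut-off.

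**Protocol wording.** Taken literally as any decrease in any dose, the inert-drug rate is 1 − 0.5⁴ = 93.75%.

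**The case against.** The best defence is that this is a small dose-finding phase. The SAP openly waives significance, and a placebo-controlled phase is planned after a Go. A permissive screen is a legitimate choice, and confirm may mean no more than that a preset criterion was met. This stands as a reason to leave the cut-off and sample size alone. It does not supply the missing error rate, and it supports describing a Go as a screen.

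Second, under the cross-sectional reading the ICC does drive the false-Go rate, so it is not irrelevant on every reading. That is right. At 0.85, however, it still leaves about one false Go in two, so it is insufficient there and cancels out under the rule as written.

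Third, a true effect of 0.33 cross-sectional SD equals 0.60 SD of change. Judged by the written rule, P(Go) is then 88% (one dose) or 99% (all four), and the active dose ranks first in 59% of Gos. This softens the picture, but the odds multipliers are still only 0.883/0.741 = 1.19 and 0.989/0.741 = 1.33.

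Fourth, neither document says that the dose with the largest CBV decrease goes forward, and the secondary Glx analysis could inform that choice. The 43% therefore describes the CBV ranking only and does not predict which dose would be chosen. Glx may add evidence, but the Go rule does not use it.

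**Conclusion.** The concern holds. Under the written rule a Go is the likely result with or without an effect: about 74% for an inert drug, against 82% or 94% for effects at the target. No effect, whatever its size, can make a Go raise the odds by more than a factor of about 1.35. On the cross-sectional reading at ICC 0.85 the inert-drug rate is 47% to 50%, against 70% and 93%; that discriminates better but is still not confirmation. The ICC does not by itself justify three patients per dose on either reading.

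These figures rest on normality, independence, a common SD and no drift. The cross-sectional figures also rest on the ICC of 0.85, which comes from only four patients.

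**What to change.** Changes to the SAP's Go No-Go paragraph:

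1. Remove the claim that the ICC justifies three patients per dose, and state the actual basis for that number.
2. State which SD the 0.33 refers to.
3. Give the operating characteristics beside the rule, with their assumptions. As written, P(Go) is about 74% with no effect, 82% with one dose at a true decrease of 0.33 SD of change, and 94% with all four. If the cross-sectional SD is meant, give about 50%, 70% and 93% at ICC 0.85, and show how the first figure moves with the ICC.
4. Replace the confirmation wording with a statement that a Go is a permissive screen for the placebo-controlled phase and does not confirm that a dose engages the target.
5. Report each dose's mean change with its 95% CI from the planned ANOVA.

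The Protocol's Go/No-Go sentence, which carries no threshold, should be reconciled with the SAP at the same time.

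The cost is wording and a few intervals from an analysis already planned. No patients or scans are added, and if the written rule is kept P(Go) is unchanged. What is given up is the right to report a Go as a confirmed hypothesis.
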